4 BACKGROUND

In neuromuscular diseases, muscular involvement is extremely heterogeneous. The high variability is not only present in various neuromuscular diseases, but also within one type of disease itself. Since phenotypes vary among affected patients, a long delay between the onset of symptoms and diagnosis is common in neuromuscular disorders [1]. In myotonic dystrophies, specific muscles are affected by myotonia and stiffness, whereas other muscles or muscle groups may not or only be slightly affected or may show signs of weakness and atrophy [2]. In non-dystrophic myotonia like congenital myotonia Becker and Thomson, a generalized muscles stiffness is present in almost all patients at younger ages. For dystrophic and non-dystrophic myotonia, hallmarks are a delayed relaxation and stiffness of affected muscles after voluntary contraction [3, 4], but phenotypes show high variability. Non-invasively, myotonia and muscle stiffness is typically only described clinically, but not objectively measured. Semi-invasively, the severity of myotonia can be assessed by electromyography, requiring a high logistic and technical effort including sophisticated computerized measurements, which makes implementation in clinical practice almost impossible. In several Limb-girdle-muscular dystrophies (LGMD), muscles are selectively affected by fatty infiltration and atrophy. This becomes most evident in autosomal recessive LGMD2L, where the medial gastrocnemius muscles are selectively affected by fatty infiltration and atrophy at early stages of the disease, while proximal muscles are more likely to cause myalgia and reduced muscular endurance, but do not show signs of fatty infiltration [5]. In Late-Onset Pompe disease (LOPD), abdominal and paraspinal muscles are early and primarily affected [6-8]. In contrast, affection of the second motoneuron (Amyotrophic lateral sclerosis (ALS); spinal muscular atrophy (SMA)) as well as diseases with affection of the peripheral nervous system (chronic inflammatory demyelinating polyneuropathy (CIDP) or different forms of hereditary sensory and motor neuropathies (HMSN)) cause muscular atrophy without signs fatty infiltration, but are associated with muscular cramps in the majority of cases [9-12]. For assessing fatty infiltration of muscles or muscular atrophy, magnetic resonance imaging (MRI) is increasingly used as a complement to clinical and electrophysiological examination in neuromuscular disease, but costs and time are limitations [13]. Muscle ultrasound has proven to have a high sensitivity and specificity for characterizing and detecting neuromuscular disorders but is always complementary to clinical and electrophysiological findings [14]. It may be useful to detect and describe muscular movements like fasciculations and myokymia, but a correlation of myotonia or muscle stiffness with clinical disease severity is poor [15, 16].

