5 STUDY OBJECTIVES

5.1 Primary Objective

The primary objective of this study is to assess stiffness, muscle tone, relaxation periods and elasticity of various muscles in patients with dystrophic or non-dystrophic myotonia.

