6.3 Number of patients

Approximately 70 patients will be enrolled, about 3-5 each in the following disease groups: Limb-Girdle-Muscular Dystrophy (LGMD), Myotonic Dystrophies Type 1 and 2 (DM1, DM2), Late-Onset-Pompe Disease (LOPD), Distal Myopathies, Congenital Myotonia, Spinal muscular atrophy Type 3 (SMA3), Amyotrophic lateral sclerosis (ALS) and peripheral Polyneuropathies (CIDP, HMSN). 20 healthy age- and gender-matched patients will be enrolled as a control group.

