7.3 Discussion of Study Design, Including Choice of Control Group

This is a monocentric, blinded, cross-sectional explorative study designed to evaluate myotonia, muscle stiffness and elasticity in 70 patients with neuromuscular disorders. For statistical comparison, we plan to recruit 20 healthy subjects as a control group.

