10.2 Determination of Sample Size

50 patients and 20 healthy subjects will be enrolled in this study. No formal sample size calculations have been performed. This is an exploratory pilot-study and is not powered to make any statistical inferences.

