10.3 Demographics and Baseline Characteristics

Demographic and baseline data on medical history and neuromuscular disease history as well as patient-related data will be summarized using exploratory and descriptive statistics for continuous variables and frequency distribution for categorical variables. To compare the mean values of two groups, the t-test will be used, to compare frequencies between two groups, the chi-square test. Correlations are calculated by using the Spearman and Pearson coefficient.

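### The 20 controls are called matched on age and gender, but no patient group is named as the target and no selection step is given, so a comparison of any disease group with controls by the unadjusted t-test is open to age and sex confounding

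*Protocol*

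**What the plan says.** Protocol section 6.3 plans "Approximately 70 patients will be enrolled, about 3-5 each in the following disease groups". The list that follows has ten entities if DM1 and DM2, and CIDP and HMSN, are counted separately. The section then states "20 healthy age- and gender-matched patients will be enrolled as a control group"; the synopsis says the same with an approximate 20. Section 7.3 gives the purpose: "For statistical comparison, we plan to recruit 20 healthy subjects as a control group".

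No section says which patients the controls are matched to, at what ratio or within what age limits. Section 6.1 asks of healthy volunteers only adult age, consent and no clinical sign of neuromuscular disease. Section 6.4 gives patients' relatives, approached at routine appointments, as an example of where volunteers come from.

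On method, section 10.3 (demographics and baseline characteristics) says "To compare the mean values of two groups, the t-test will be used". It names no covariate and no pairing. Section 10.1 rules out formal inferential tests, and section 10.2 says "No formal sample size calculations have been performed". The primary objective in 5.1 is to "assess stiffness, muscle tone, relaxation periods and elasticity of various muscles in patients with dystrophic or non-dystrophic myotonia"; it mentions no control group. Age and gender are collected at visit 1 (7.1.2).

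**The concern.** Matching is the only protection against age and sex imbalance that the protocol offers for its patient-control comparison, and it has no stated target. Controls balanced against the whole patient mix could still differ in age or sex from any one disease group, because the list joins conditions that may present at different ages. Section 4 says of non-dystrophic myotonia that "a generalized muscles stiffness is present in almost all patients at younger ages", while the list also includes a form of Pompe disease defined by late onset.

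If stiffness, tone or elasticity readings vary with age or sex, a difference between a disease group and the controls could partly reflect demographics, or be masked by them. This holds for a described difference in means as much as for a test. It also affects how the disease-group reference values of section 5.2 read against healthy values.

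**Working it through.** **Inputs from the protocol.** 20 controls (6.3, 7.3, 10.2); 50 patients (7.1, 10.2); about 3-5 patients per disease group (6.3); ten entities by the count above; three of them myotonic (DM1, DM2, congenital myotonia).

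**The plan's own total.** 10 × 5 = 50 patients, and 50 + 20 = 70 people, which agrees with "50 patients and 20 healthy subjects will be enrolled in this study". At the lower end, 10 × 3 = 30 patients. The figure of about 70 patients in 6.3 and 7.3 fits this arithmetic only if the 20 controls are counted in it.

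**Can the controls be matched individually to all patients?** 20/50 = 0.40 controls per patient, or 20/70 = 0.29 if 70 is read as patients alone. One-to-one matching is impossible either way. Spread evenly, there are 20/10 = 2 controls per disease entity.

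**Can they be matched to the myotonia patients?** 3 × 3 = 9 to 3 × 5 = 15 patients. 20/15 = 1.3 to 20/9 = 2.2 controls per patient. In number, yes.

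**What if they are matched to the overall mix?** With ten equal groups, three of them myotonic, the pool mean age is 0.3 × (myotonia mean) + 0.7 × (mean of the others). The gap between myotonia patients and controls is then 0.7 × (gap between myotonia and other patients). Assumed gaps of 0, 5, 10 and 20 years give 0, 3.5, 7 and 14 years.

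**Effect on an unadjusted t-test (assumption-based).** The protocol gives no age distribution and no association of age with the readings. Assume that controls and myotonia patients differ by 15 years and that a reading drifts by 0.01 to 0.03 SD per year: bias b = 15 × 0.01 = 0.15 SD to 15 × 0.03 = 0.45 SD. With no true disease effect, the t statistic is noncentral with noncentrality b / √(1/n + 1/20) and n + 18 degrees of freedom. Two-sided 5% level:

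| Bias (SD) | 15 vs 20 (√ term 0.342) | 9 vs 20 (√ term 0.401) |
|---|---|---|
| 0 | 5.0% | 5.0% |
| 0.15 | 7.1% | 6.5% |
| 0.30 | 13.7% | 11.1% |
| 0.45 | 24.9% | 19.1% |

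The 15-year gap is at the high end: under pool matching it needs myotonia patients to differ from the others by 15/0.7 ≈ 21 years.

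**A second set of assumptions.** With an age SD of 15 years, a correlation of 0.1 to 0.5 between age and reading, and a gap of 0 to 15 years, bias = correlation × gap / 15, which is 0 to 0.50 SD. By normal approximation with 15 vs 20, the error is 5% to 31%; correlation 0.3 with a 10-year gap gives 0.20 SD and 9%.

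**Sex.** An assumed sex effect of 0.3 to 0.8 SD times a difference in male share of 0 to 0.3 gives a bias of 0 to 0.24 SD.

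**The case against.** The strongest reply is that the text does not say what a critic may read into it. Four parts of it stand.

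- A reader might infer that the controls are matched to the pool of ten diseases and therefore to no single group. Section 6.3 names no target at all. It does not exclude matching to the myotonia patients, for whom 20 controls suffice in number.
- A reader might infer that the primary comparison is confounded. The primary objective is descriptive and contains no contrast with controls, and sections 10.1 and 10.2 disclaim formal inference. The patient-control comparison comes from 7.3, which does not say which patients are compared.
- No age or sex distribution is given. The remark in section 4 about younger ages describes the disease, not the enrolled adults, so neither the size nor the direction of a gap is known. It may be zero.
- The t-test sentence stands under demographics and baseline, and a statistical analysis plan that is not shown could specify adjustment. Relatives are only an example of a source and do not cancel the matching requirement in 6.3.

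The reply does not remove the point. The choice of whom to match governs recruitment and must be made before controls are enrolled. Later adjustment cannot create age or sex overlap that was never recruited. The t-test is also the only method that the protocol names for comparing two means, and a difference in means carries the same bias whether or not a p-value is printed.

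**Conclusion.** The point holds as a gap in the design: matching is promised without a target or a procedure, and the named two-group method neither adjusts for age and sex nor uses the matching. One set of 20 cannot be assumed balanced with the 9 to 15 myotonia patients or with any other single disease group, so a difference between such a group and the controls is open to age and sex confounding.

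The documents do not support saying that such a comparison is confounded, or that the controls are matched to no group. The error range of about 7% to 25% (15 vs 20) rests entirely on the assumed 15-year gap and drift per year, and there is no inflation if the distributions agree. In an exploratory study the main consequence is for how differences and reference values are read, rather than for a formal error rate. The change is worth making because it costs little and its recruitment part cannot be made later.

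**What to change.** **Section 10.3.** For patient-control differences in the MyotonPro readings, replace the unadjusted t-test with an estimate adjusted for age and sex, for example a linear model with group, age and sex, giving the difference and its 95% confidence interval, reported descriptively. Both covariates are already collected at visit 1. With 9 to 15 myotonia patients and 20 controls the model uses 29 to 35 people and four coefficients, leaving 25 to 31 residual degrees of freedom.

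**Sections 6.3 and 7.3.** Name the matching target. The preferred choice is frequency matching by sex and age band to the patients of the primary objective (DM1, DM2, congenital myotonia), with the remaining controls spread over the ages of the other groups. Do not describe the controls as matched for any other comparison.

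**Cost.** No added participants or tests. Some willing relatives will not fit an open slot, so control recruitment slows slightly. If 15 controls are tied one-to-one to myotonia patients, 20 − 15 = 5 are left to cover the ages of the seven other disease entities (11 if there are only 9 myotonia patients). For those groups adjustment is then the main protection, and it is weak where control ages do not overlap with theirs.

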6.4 Recruitment

Patients will be asked to participate during their routine treatment at the in-patient clinic of the Friedrich-Baur-Institute or will be asked during appointments at the out-patient-clinic of the Friedrich-Baur-Institute. Healthy volunteers (e.g. relatives from patients) will be asked to participate during routine appointments of their relatives.

7 INVESTIGATIONAL PLAN

7.1 Study Design

This is a cross-sectional, blinded, monocentric, explorative study to evaluate the stiffness, muscle tone, relaxation periods and elasticity of various muscles in patients with neuromuscular diseases. Local ethic's approval is obligatory before the recruitment of the first patient. The patient must provide informed consent prior to performing any protocol-related procedure at the screening visit. The estimated duration of this study is 12 months or as soon as a total of 50 patients with neuromuscular diseases and 20 healthy volunteers are evaluated. The person assessing the muscle stiffness and myotonia, using the MyotonPro® device, will be blinded to the diagnosis, to medical history as well as results from the clinical tests (clinical muscle strength, 6-minute-walk-test) and results of muscle ultrasound assessments. The study duration for one patient or one healthy volunteer is two to a maximum of seven days. All relevant data will be assessed within visit 1. At the second visit (visit 2), only measurements of the MyotonPro® will be repeated to evaluate the reliability of the measurements.

Both patients and healthy volunteers will perform the following assessments:

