
To assess myotonia and muscle stiffness in neuromuscular disorders, we use a handheld device that allows non-invasive measurement of relaxation time, stiffness and elasticity. For this, the MyotonPro®, a commercially available device, is used to evaluate the stiffness, myotonia and elasticity of muscle fibers by applying short pulses to the underlying tissue [17]. Its validity and reliability were proven in a large cohort

of healthy volunteers as well as patients with different types of muscle diseases [17-22]. A brief pulse of a few seconds causes the underlying tissue to oscillate and send back a signal that is picked up and processed by the device. This allows to evaluate relaxation time, stiffness and elasticity of the tissue and may help to assess the severity of myotonia and stiffness in neuromuscular patients. The following measurements will be performed automatically, analyzing the oscillation curves and calculating the tissue tone (frequency (Hz)), the tissue stiffness (N/m), the decrement as parameter for the elastic stiffness of the tissue and viscoelastic parameters like relaxation time (in milliseconds) and creep as non-elastic tissue strain. The device has recently been used in patients with altered muscle elasticity and stiffness like Parkinson's disease, stroke and Duchenne muscular dystrophy [19-21, 23-25] as well as assessing muscular atrophy and viscoelasticity due to immobility in healthy subjects [22].

So far, the knowledge of muscle elasticity, myotonia and stiffness in various neuromuscular diseases is scarce. The study aims to test elasticity, myotonia and stiffness in various neuromuscular diseases and to provide reference values for different neuromuscular disease groups.

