7.1.4 MyotonPro® Device

The MyotonPro® Device is a commercially available electronic device for non-invasive measurement of muscle stiffness, muscle tone, relaxation periods and viscoelasticity. The method of measurement consists of recording damped natural oscillation of soft biological tissue in the form of an acceleration signal and the subsequent

simultaneous computation of the parameters of State of Tension, Biomechanical and Viscoelastic properties. A damped natural oscillation is induced by an exterior, low force quick-release mechanical impulse under constant pre-load. The tip of the myometer will be placed on the tissue perpendicular to the underlying muscle. The device gets activated by a slight pressure on the tip which exerts a local impact on the tissue utilizing a brief mechanical impulse. This causes a minor deformation of the underlying muscle tissue. After the impact, the tip is quickly released, and the damped oscillatory behaviour of the tissue will be recorded by an accelerometer in the device. The viscoelastic stiffness of the underlying tissue will automatically be calculated using the following equations (S=stiffness; D=elasticity; R=relaxation):

$$S = \frac{a_{max} \cdot m_{probe}}{\Delta l} \quad D = \ln \left(\frac{a_1}{a_3} \right) \quad R = t_R - t_1$$

S stands for stiffness, measured in N/m, and is the biomechanical property of a muscle that characterizes the resistance to a contraction or to an external force that deforms its initial shape. Elasticity **D** is the logarithmic decrement of a tissue's natural oscillation. Elasticity is the biomechanical property of a muscle that characterizes the ability to recover its initial shape after a contraction or removal of an external force of deformation. The Relaxation **R** is the time for a muscle to recover its shape from deformation. The functionality of the MyotonPro®, its way of measurement and the calculations have been tested and validated in a high number of clinical studies. Therefore, this study is not intended to validate the measurements of the MyotonPro® device itself nor its safety and accuracy of measurements, but to evaluate measurement results in patients with neuromuscular diseases and elaborate reference values.

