7.1.6. Semiquantitative muscle ultrasound

Muscle ultrasound is an ideal imaging modality that allows for atraumatic, noninvasive, radiation-free point-of-care neuromuscular imaging [28]. Muscular dystrophies are typically associated with an increase in the echogenicity from the muscle substance, distal attenuation of muscle echo and a corresponding loss of bone echo. Spinal muscular atrophies and neuropathies also showed an increase in muscle echo along with atrophy of the muscle and increase in depth of subcutaneous tissue, but a persisting bone echo. In several other myopathies, similar changes are seen [29]. In semi-quantitative muscle ultrasound, muscle intensity will be documented using the 4-point Heckmatt score [28].

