10.5 MyotonPro® measurement reliability

To ensure high reliability in measurements performed with the MyotonPro® device, a second measurement will be performed within 1-7 days after visit 1 (Test-Retest). The degree of similarity between the two measurements is determined by computing a correlation coefficient. In addition, 95% confidence intervals will be used to estimate the change from baseline to the second study visit. All data will be presented by study visit in by-patient listings.

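### The blinding rule covers only the MyotonPro operator: no masking is stated for the visual Heckmatt grade, and the operator's list omits the visit 1 readings used in the retest

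*Protocol*

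**What the plan says.** **Who is masked.** Section 7.1 holds the only blinding rule in the available text, and it names one person, the MyotonPro operator, who "will be blinded to the diagnosis, to medical history as well as results from the clinical tests". The clinical tests are strength and the walk test, and the list ends with the ultrasound results. Visit 1 device readings are not on it. The synopsis, Section 7.1 and Section 7.3 call the study blinded without adding detail.

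**Ultrasound.** Section 7.1.2 asks for thickness in millimetres and an echogenicity grade of I to IV. Section 7.1.6 says that "muscle intensity will be documented using the 4-point Heckmatt score". Neither says who grades or what that person may know. Section 7.1.2 puts diagnosis, walk test and MRC strength in the same visit and lists them before ultrasound. Section 7.1.6 describes increased muscle echo in dystrophies, spinal muscular atrophies and neuropathies, and similar changes in several other myopathies. The fourth secondary objective (Section 5.2) correlates echogenicity, subcutaneous fat and muscle thickness with the device values.

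**Retest.** At visit 2, 1 to 7 days later, "only measurements of the MyotonPro® will be repeated to evaluate the reliability of the measurements". Section 10.5 adds: "The degree of similarity between the two measurements is determined by computing a correlation coefficient", together with a 95% confidence interval for the change. Section 4 says of the device: "The following measurements will be performed automatically, analyzing the oscillation curves". Placement is manual, however: "The tip of the myometer will be placed on the tissue perpendicular to the underlying muscle" (Section 7.1.4), and pressing the tip triggers the reading. Section 7.1.3 gives database access to those directly involved in the study and makes no exception for the operator.

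**The concern.** The masking is attached to the measurement that leaves the assessor least room for judgement. The measurement that is wholly a judgement has none stated. The fourth objective pairs the two, so the device side of the correlation is protected and the echogenicity side is not. If the grader knows that someone is a patient, or which disease the patient has, grades can drift towards what that status predicts. Where device values also differ between those groups, part of the reported correlation would come from the grader's knowledge and not from the muscle. No later analysis can separate the two.

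The retest raises a similar but smaller question. Visit 2 exists only to show reliability. An operator with the first values in view could re-place the probe, or repeat a reading that looks out of line, and bring the second value closer to the first. Section 7.1.4 sets no number of readings per site and no rule for repeats, so nothing in the text prevents this.

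**Working it through.** The plan states no figure on this point, so there is none to reproduce. The check is a comparison of the text, a count of what is exposed, and two illustrations under labelled assumptions.

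**1. Text side by side**

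| Measurement | Room for assessor judgement | Masking stated | Use |
|---|---|---|---|
| MyotonPro, visit 1 | Placement and trigger only; values computed | Diagnosis, history, clinical tests, ultrasound | All objectives |
| MyotonPro, visit 2 | Same | Same list; visit 1 readings not included | Reliability (10.5) |
| Heckmatt I-IV | Whole value is a visual grade | None | Fourth secondary objective |
| Thickness (mm) | Caliper-type measurement | None | Fourth secondary objective |

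**2. Exposure**
- Sites: 8 muscles x 2 sides = 16, the same for ultrasound and device.
- With 50 + 20 = 70 participants (Sections 7.1 and 10.2): 16 x 70 = 1,120 Heckmatt grades at visit 1 and 1,120 retest sites at visit 2.
- Sections 6.3 and 7.3 instead give 70 patients plus 20 controls: 16 x 90 = 1,440 of each.
- Values an operator would have to recall: 16 sites x 3 parameters = 48 per participant per visit.

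**3. Illustration for the Heckmatt grade (assumed inputs)**

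Suppose that the true correlation of echogenicity with the device value is 0 and that echogenicity is unrelated to group. The grade shifts by k SD for each SD of the group mean of the device value, and η² is the share of device variance lying between groups. Then the pooled correlation is

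r_obs = k√η² / √(1 + k²).

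| η² | k = 0.25 | k = 0.5 | k = 1.0 |
|---|---|---|---|
| 0.1 | 0.077 | 0.141 | 0.224 |
| 0.2 | 0.108 | 0.200 | 0.316 |
| 0.4 | 0.153 | 0.283 | 0.447 |

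These are absolute sizes. The sign is positive if grades shift the same way as device values across groups, and negative otherwise. If η² = 0, the spurious term is zero. The mechanism therefore works mainly when groups are pooled.

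**4. Illustration for the retest (assumed inputs)**

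Suppose that the recorded visit 2 value is (1 − w) x the true visit 2 value + w x the visit 1 value, with equal variances and true retest correlation r. Then

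r_obs = [(1 − w)r + w] / √[(1 − w)² + w² + 2w(1 − w)r].

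For r = 0.7 and w = 0.1: (0.63 + 0.1) / √(0.81 + 0.01 + 0.126) = 0.73 / √0.946 = 0.751.

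| True r | w = 0.1 | w = 0.2 | w = 0.3 |
|---|---|---|---|
| 0.6 | 0.664 | 0.728 | 0.789 |
| 0.7 | 0.751 | 0.799 | 0.845 |
| 0.8 | 0.835 | 0.868 | 0.899 |
| 0.9 | 0.918 | 0.935 | 0.950 |

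Here the direction is fixed: any pull towards visit 1 raises the coefficient. None of k, η², w or r comes from the protocol.

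**The case against.** - **These are silences.** The protocol nowhere says that the grader will know the diagnosis or that the operator will see earlier values. Section 3 (Responsibilities) was not available and could assign assessors. A reader might infer that grading is unblinded; the text does not support that. It supports only that no masking is stated where the blinding rule is set out or where the procedures are described.
- **The retest route is narrow.** The device computes its values under constant pre-load, and recalling 48 values over 1 to 7 days is hard. The protocol does not say whether the same person measures at both visits. If not, recall disappears, and only sight of recorded values is left. This stands, and it is why the retest is the secondary point. A reader might infer that the reliability coefficient will be inflated; the documents support only that it could be.
- **Section 7.1.6 does not separate diseases by echogenicity.** It expects an increase in most patient groups and distinguishes them by bone echo and atrophy. This stands. The expectation it creates is mainly patient versus control, so a claim that grading would strengthen between-disease association goes too far. A true correlation could equally be weakened.
- **The study is exploratory, not powered for inference, and not meant to validate the device.** This limits the consequences but does not answer the point. The correlations and the retest coefficient are planned outputs, and an exploratory label does not remove assessor bias.

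**Conclusion.** The point holds in a limited form. As written, the blinding rule leaves the Heckmatt grade without stated protection, so the echogenicity part of the fourth secondary objective is open to avoidable observer bias. The direction depends on how device values differ between groups. The millimetre measurements in the same objective are much less exposed, and the device side is already protected by Section 7.1. Second and smaller, omitting the visit 1 readings from the operator's list leaves room for test-retest agreement to be overstated.

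The documents give no size for either effect. Under the assumed ranges above, a true correlation of 0 could appear as 0.08 to 0.45 in absolute value, and a true retest correlation of 0.70 as 0.75 to 0.85. These figures show only that modest influence could matter; they are not estimates for this study. The 1,120 grades and 1,120 retest sites (1,440 of each under the larger enrolment figure) count exposure, not bias. The conclusion assumes that Section 3 contains no masking of these assessors. Masking of assessors belongs in the protocol, and it should be settled before the first participant is measured.

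**What to change.** **Section 7.1.6.** Store the ultrasound images under the pseudonym. Have the study's ultrasound reader assign the Heckmatt grade from them in mixed order, patients and controls together, without diagnosis, clinical results or device values.

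**Section 7.1.** Add to the operator's blinding list: 'and to all visit 1 MyotonPro readings'. Record visit 2 on a separate CRF page, and give the operator no database view of visit 1 values until visit 2 is entered. State whether the same person measures at both visits.

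**Cost.** Image storage, a short delay in grading, a split CRF page and two short text changes. No extra visits or participants are needed. If the person who scanned the participant also grades, some recall remains; mixed order reduces it but does not remove it. If images are not stored, masked grading cannot be recovered afterwards.
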